3.1 Hypotheses

We hypothesize that our 6-week mental imagery training protocol will improve goal-directed cognitive functioning in everyday life of PD patients. Furthermore, we predict the effects of mental imagery will increase task-specific whole-brain functional connectivity and improved differentiation of core brain networks. We hypothesize that the training effects on A)

goal-directed cognitive functioning and B) functional network re-organization will be sustained over the course of 12 weeks post-intervention in the PD-MI group, but not in the PD-Con group.

Lastly, we hypothesize that the putative task-specific within- and between-network functional connectivity changes in the PD-MI group at the 6- and 12- week timepoints will predict the corresponding self-reported, performance-based, and executive function test outcomes.

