4.2 Outcome Variables

4.2.1 Primary Outcome Variables

1) Quality of life in Neurological Disorders (Neuro-QoL) Scores

Timeframe: This measure will be collected at baseline (T0), immediately after 6 weeks of intervention (T1), and 12 weeks thereafter (T2) from all subjects.

Rationale: The Neuro-QoL is a set of self-report measures that assesses the health-related quality of life of adults and children with neurological disorders. Neuro-QoL instruments were developed through a collaborative, multisite NINDS-sponsored research initiative to construct psychometrically-sound and clinically-relevant health-related quality of life measurement tools for individuals with neurological conditions including PD. The Neuro-QoL instruments enable within-disease as well as cross-disease comparisons and are intended for use in both neurology clinical trials and clinical practice. We will use the Neuro-QoL version 2 Cognitive Function item bank to assess post-training self-reported changes in cognitive functions.

Change in the Neuro-QoL version 2 Cognitive Function scores from T0 to T1 and across T2 will be the primary cognitive outcomes of this study. Significant increase in the Cognitive Function scores at T1 will be considered significant improvement in self-reported cognitive function in everyday life. Significant increase in these scores across T2 will be considered sustained improvement in self-reported cognitive function in everyday life.

2) Questionnaire on Mental Imagery (QMI) Vividness of Imagery Scale scores

Time frame: This measure will be collected at baseline (T0), immediately after 6 weeks of intervention (T1), and 12 weeks thereafter (T2) from all subjects.

Rationale: The QMI is a measure of vividness of an individual's multisensory and motor imagery on a scale of 1 to 7 (1: perfectly vivid image, 7: no image present at all).

Change in the QMI scores from T0 to T1 and across T2 will serve as the manipulation check for the mental imagery intervention. Significant increase in these scores at T1 will be considered improved imagery vividness. Significant increase in these scores across T2 will be considered sustained improvement in imagery vividness.

3) Task-specific whole-brain pairwise functional connectivity

Time frame: This measure will be collected at baseline (T0), immediately after 6 weeks of intervention (T1), and 12 weeks thereafter (T2) from all subjects.

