The primary, secondary and exploratory outcomes as outlined in Aims 1 and 2 will also apply to Aim 3. All cognitive and functional MRI tasks will be repeated 12 weeks after the completion of the training program (Visit 4). These results will then be compared with those obtained at baseline and 6-week post-intervention using a 3x2 mixed ANOVA with an interaction term (dependent variables: cognitive test scores and functional connectivity and graph measures, between-subject factor: group, within-subject factor: time with three levels, i.e., baseline, 6-weeks post-intervention, and 12-weeks post-completion, interaction: group-by-time) ($p < 0.05$, two-tailed). A significant interaction will be followed by post hoc simple effects tests to determine the level(s) of interaction.

AIM 4: To explore the brain-cognition link associated with mental imagery training in PD

Exploratory Aim: We will examine the post-training brain-cognition relationship at the 6-week and 12-week timepoints in each group. We will test whether the post-training changes in task-specific whole-brain pairwise functional connectivity and graph measurements will predict the post-training differences in the Neuro-QoL Cognitive Function and composite executive test scores in each group.

Exploratory outcomes: This brain-behavior relationship at 6 weeks will be the exploratory outcome of Aim 2 and that at 12 weeks will be the exploratory outcome of Aim 3.

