5.4.2 Sample Size Considerations

We calculated the sample size based on the primary cognitive outcome, i.e., Neuro-QoL version 2 Cognitive Function scores. The Neuro-QoL Cognitive Function validation study with 120 PD patients who had mild disease (Hoehn & Yahr stage 2) showed mean \pm SD = 50.46 \pm

7.25.⁹⁷ A change of 2-6 T-scores have been considered a minimally important change in patient-reported outcome measures.¹⁰³

We estimated the sample size based on the assumption that there will be an average of 4 T-score improvement after mental imagery training using the G*Power 3.1 software^{104,105}. The repeated-measures ANOVA between-subject factor model with two groups and two measurements, with an effect size of $f=0.266$ (corresponding to a moderate effect size $d=0.53$), alpha 0.05, and power 0.80 yielded a total sample size of 86 (43 in each group). With an estimated 15% drop out ($86/0.85 \approx 101$) during the 6-week intervention period and another 15% drop out ($101/0.85 \approx 120$) in the subsequent 12-week period, we plan to recruit 120 subjects in total.

In our previous work with PD patients using motor (N=22) and visual (N=22) imagery training, we showed robust task-specific pairwise functional connectivity changes post-training especially in the respective motor and visual networks.⁴ Therefore, we think this sample size will also be adequate for the primary imaging outcome.

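### Aim 3 names no between-arm test of durability: 'sustained' rests on an omnibus interaction, unspecified simple effects and a success rule without a comparator

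*Combined protocol and SAP*

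**What the plan says.** Section 5.4.1 (Aim 3) compares Visit 4 with baseline and Visit 3 "using a 3x2 mixed ANOVA with an interaction term", with "within-subject factor: time with three levels, i.e., baseline, 6-weeks post-intervention, and 12-weeks post-completion, interaction: group-by-time", at a two-tailed 0.05 level. The follow-up is one sentence: "A significant interaction will be followed by post hoc simple effects tests to determine the level(s) of interaction." It gives no deciding contrast, reference visit, direction or multiplicity rule.

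The criterion for success is in section 4.2.1. For Neuro-QoL it reads: "Significant increase in these scores across T2 will be considered sustained improvement in self-reported cognitive function in everyday life." The Synopsis and section 4.2.2 use matching sentences for the other outcomes. None of them names a comparator.

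Section 3.1 hypothesises that the training effects will be "sustained over the course of 12 weeks post-intervention in the PD-MI group, but not in the PD-Con group."

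Durability is the secondary objective (section 3.3).

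**The concern.** A claim of durability in a two-arm trial should rest on the difference between arms at the later visit, relative to baseline. No sentence in the plan requires that comparison. The two-degree-of-freedom interaction asks only whether the arms differ in their pattern over three visits, and an effect at T1 alone can make it significant. The rest is left to a follow-up that could be any of these:

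- PD-MI against PD-Con at T2;
- the T0-T2 change within PD-MI;
- significance in PD-MI but not in PD-Con;
- the between-arm difference in T0-T2 change.

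These have very different error rates and power, and the choice could be made after the data are seen. At stake is whether a gain that both arms share is reported as a lasting effect of imagery training, or a lasting effect is missed.

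**Working it through.** **The plan's own figure.** Section 5.4.2 gives no power for Aim 3. Its 86 ("alpha 0.05, and power 0.80 yielded a total sample size of 86 (43 in each group") is for a between-subject factor with two measurements: λ = f²·N·m / [1 + (m−1)ρ] = 0.266² × 86 × 2 / 1.5 = 8.11, power 0.804. This reproduces the stated figure if ρ = 0.5, which the documents do not state. After the two planned 15% losses, 120 × 0.85 × 0.85 = 86.7, so 43 per arm at T2 is the planned position.

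**Inputs.** From section 5.4.2: SD 7.25, a 4-point effect, 43 per arm. Assumed: equal visit correlation ρ of 0.5 or 0.7, and a gain of 0 to 3 points shared by both arms.

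**Step 1: the omnibus test.** λ = (n/2) Σ(δₜ − δ̄)² / [σ²(1 − ρ)], where δₜ is the between-arm effect at each visit.

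- Effect gone by T2, δ = (0, 4, 0): δ̄ = 4/3 and the sum is 16/9 + 64/9 + 16/9 = 10.67.
- Effect kept, δ = (0, 4, 4): δ̄ = 8/3 and the sum is 64/9 + 16/9 + 16/9 = 10.67.
- An effect at T2 only gives the same sum.

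At ρ = 0.5, λ = 21.5 × 10.67 / (52.56 × 0.5) = 8.73 and power is 0.749. At ρ = 0.7, λ = 14.54 and power is 0.933. The test cannot tell the cases apart. This equality needs equal correlations. With assumed correlations of 0.7, 0.7 and 0.5 (T0-T1, T1-T2, T0-T2), rejection is about 93% for T1 only and 85-86% for T2 only or both.

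**Step 2: effect gone at T2, within-arm readings** (simulated; separate runs agree to within about two percentage points).

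| Shared gain kept by both arms | Interaction and PD-MI rise T0-T2, ρ = 0.5 / 0.7 | Same, and no significant rise in PD-Con |
|---|---|---|
| 0 | 2% / 3% | 2% / 3% |
| 1 | 11% / 20% | 10% / 16% |
| 2 | 32% / 59% | 19% / 23% |
| 3 | 57% / 86% | 15% / 6% |

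The last column also fails in the other direction. A truly kept 4-point effect with a 3-point shared gain is recognised in only about 23% / 7% of trials.

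**Step 3: between-arm readings.**

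- Direct contrast of T0-T2 change: SE = σ√[4(1 − ρ)/n] = 7.25 × √(2/43) = 1.564 at ρ = 0.5 and 7.25 × √(1.2/43) = 1.211 at ρ = 0.7. The ratios 4/1.564 = 2.56 and 4/1.211 = 3.30 give power 0.715 and 0.904. A false favourable claim occurs in about 2.5% of trials.
- The same contrast after a significant omnibus test: power about 66% / 88%.
- Group at T2 after a significant omnibus test: false claims about 1-2%, power about 56% / 67%.

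**The case against.** The strongest defence is that the omnibus result is only a gate. The follow-up and the 'across T2' condition still have to be met. The follow-up sentence fits a group comparison at each visit just as well as a within-arm test, and Aims 1 and 2 are explicitly comparisons between the arms. Read that way, a vanished effect is called sustained in only about 1-2% of trials. This stands. A reader might infer that the plan commits itself to within-arm tests, but the documents do not say so.

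A reader might also take 32-57% / 59-86% as the plan's error rate. That range needs the within-PD-MI reading, a shared gain of 2-3 points, and no use of the 'not in PD-Con' half of the hypothesis. With that half applied the rates are 15-19% / 6-23%, and with no shared gain they are 2-3%. The documents make a shared gain plausible: section 1.2 reports improvement in both groups of the earlier imagery trial, and section 2.3.2 expects controls to benefit from psychoeducation. They give no size for it on Neuro-QoL.

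Reading 'across T2' as T1 to T2 would make a fully retained, flat gain fail. That reading is strained, because the full phrase in section 4.2.1 runs more naturally from T0 through T2.

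Gating pairwise tests on an omnibus test is conventional, and its cost to the direct contrast is modest (72% to 66% at ρ = 0.5, 90% to 88% at 0.7).

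What remains is that the plan does not name the deciding contrast, and the candidates perform very differently.

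**Conclusion.** The point holds as a gap in specification. Aim 3 does not test durability directly, and its written success rule has no between-arm comparator. The documents do not show that a vanished effect would be declared sustained, only that some open readings allow it. Under those readings the false-claim rate runs from about 2% to 86%, depending on the shared gain, the correlation and whether PD-Con must be non-significant.

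The direct contrast is better than each alternative in at least one respect. It removes the false claims of the within-arm readings. For a kept effect it has more power than a gated group comparison at T2 (72% against 56% at ρ = 0.5, 90% against 67% at 0.7). Its own power depends on the correlation and is about 57% at ρ = 0.3. All figures assume SD 7.25, 43 per arm and equal visit correlations. The shared gain and the correlations are assumptions throughout. I rate this a cheap improvement, with medium confidence.

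**What to change.** - In section 5.4.1 (Aim 3), define sustained improvement as PD-MI minus PD-Con in change from T0 to T2. Estimate it with a confidence interval from the three-visit model and test it directly, not conditional on the omnibus interaction.
- Use two-sided 0.05 for the cognitive outcomes. For connectivity and graph measures, keep the FDR correction given under Aim 2.
- State the favourable direction for each outcome. On the QMI a lower score means more vivid imagery, so a single rule of 'increase' cannot serve all outcomes.
- Report the between-arm T1-T2 change with its confidence interval as supporting information.
- Replace the 'across T2' sentences in the Synopsis and in sections 4.2.1 and 4.2.2 with this definition.

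The cost is wording only, with the same visits, data and model. The omnibus test can still be reported but no longer acts as a gate.

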PD patients (N=120) with mild-to-moderate disease, who do not have mild cognitive impairment according to the Movement Disorders Society Level II criteria will be randomly assigned in parallel to either the experimental (mental imagery, PD-MI) or control (psychoeducation, PD-Con) group. The PD-MI group will practice mental imagery of everyday tasks in a supervised manner and via homework, whereas the PD-Con group will receive psychoeducation on cognitive functioning and brain health in PD.

The primary cognitive target engagement outcome will be the self-reported improvement on cognitive functioning during tasks of daily life. The primary neurobiological target engagement outcome will be the task-specific changes in coordinated brain network interactions during naturalistic fMRI tasks that will mimic real-world demands. We will also examine whether the putative post-training changes in cognitive function and functional connectivity will be sustained over a 12-week period. Moreover, we will explore whether the functional connectivity changes will predict the cognitive outcomes at the 6- and 12-week timepoints. We will use mixed ANOVA tests to assess the short- and longer-term changes in outcomes before and after training.

Findings will provide critical early data for longer-term efficacy trials. If successful, mental imagery can be developed into a personalized neurocognitive rehabilitation program in PD.

Primary Objective

The primary objective of this study is to determine whether mental imagery training for 6 weeks will improve everyday cognitive functions and brain functional connectivity during naturalistic fMRI tasks in people with PD.

Secondary Objective

The secondary objective of this study is to determine whether the cognitive and imaging effects of mental imagery training will be sustained after a 12-week period in people with PD.

Study Design

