- Real-world behavior is complex and multidimensional. Naturalistic fMRI paradigms representing real-world demands lend stronger ecological validity to human neuroimaging experiments.^{33,34} This study will, for the first time, examine the specific interactions within and between core brain networks supporting goal-directed cognitive functioning in PD using mental imagery and video-watching of naturalistic tasks of daily life. We will determine the changes in the coordinated network interactions as a result of training and how they relate to the cognitive changes (putative neurobiological target engagement).
- Knowledge gained from our empirically-grounded and mechanism-based approach will help us refine the mental imagery intervention and predict treatment response in PD.

Innovations in clinical applications

- The proposed training has direct therapeutic implications, and if successful, can be developed into a personalized neurocognitive rehabilitation program in PD.
- The program could also be customized to meet the needs of PD patients with MCI.

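### Exploratory Aim 4 tests the brain-cognition link separately in each arm and at the same timepoint, so it can show a within-arm association but not that the link is specific to imagery training

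*Combined protocol and SAP*

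**What the plan says.** Section 5.4.1 titles the aim "AIM 4: To explore the brain-cognition link associated with mental imagery training in PD". The analysis is described in two sentences. First: "We will examine the post-training brain-cognition relationship at the 6-week and 12-week timepoints in each group". Second, the plan will test whether the connectivity and graph changes "will predict the post-training differences in the Neuro-QoL Cognitive Function and composite executive test scores in each group".

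On timing, section 5.4.1 splits the work by timepoint: "This brain-behavior relationship at 6 weeks will be the exploratory outcome of Aim 2 and that at 12 weeks" is assigned to Aim 3. Section 3.1 states the hypothesis for the imagery arm (PD-MI), saying that connectivity changes at the 6- and 12-"week timepoints will predict the corresponding self-reported, performance-based, and executive function test outcomes". The Synopsis says only this: "Moreover, we will explore whether the functional connectivity changes will predict the cognitive outcomes at the 6- and 12-week timepoints". Section 5.1 places the follow-up scan and the follow-up cognitive measures together at Visit 3, and again at Visit 4.

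Section 5.4.1 gives no regression model, interaction term, between-arm comparison, lagged model, significance level or multiplicity rule for Aim 4. FDR correction is named only for the Aim 2 maps and graph measures. The analysis is labelled exploratory in the Synopsis and in sections 3.3, 4.2.2 and 5.4.1.

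**The concern.** Two features limit what Aim 4 can conclude.

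- **No comparison of arms.** The aim attributes the link to imagery training, but the planned tests look at PD-MI and the psychoeducation arm (PD-Con) one at a time. If PD-MI reaches significance and PD-Con does not, the natural summary is that the link is specific to imagery. That pattern is common when the two arms share exactly the same relation. The misreading is realistic: section 1.2 summarises the team's previous imagery trial by noting that motor improvement correlated with the neurofeedback signal in only one arm.
- **No time order.** The predictor and the outcome are change scores that end at the same visit. They can be associated, but neither precedes the other, so prediction is the wrong word.

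What is at stake is interpretation. Section 2.2 expects the knowledge gained to "help us refine the mental imagery intervention and predict treatment response in PD", and section 2.3.2 says that the study will inform a phase 2 trial. An imagery-specific mechanism inferred from two separate p-values would be a weak basis for either.

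**Working it through.** **Timing.** The Synopsis sentence could be read to allow 6-week connectivity change to predict 12-week cognition. The split by timepoint in section 5.4.1 and the word *corresponding* in section 3.1 both point to same-timepoint pairing, and no lagged analysis is specified anywhere.

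**The plan's own sample size (section 5.4.2).** Inputs: f = 0.266, two groups, two measurements, alpha 0.05, power 0.80. The plan states no correlation between measurements; I assume 0.5.

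- Noncentrality = N·f²·m / (1 + (m−1)·ρ) = 86 × 0.266² × 2 / 1.5 = 8.11.
- With 1 and 84 degrees of freedom, power is 0.804. The plan's 86 is reproduced.
- Dropout: 86/0.85 = 101.2 and 101/0.85 = 118.8, close to the planned 120.

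This calculation is for Neuro-QoL. None is given for Aim 4.

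**Subjects available to Aim 4.** Section 5.4.6 restricts imaging to complete cases.

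- 6 weeks: 120 × 0.85 = 102, or 51 per arm.
- 12 weeks: 120 × 0.85² = 86.7, or about 43 per arm.

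**How often only PD-MI is significant when the arms do not differ.** Assume the same true correlation r in both arms, one pre-chosen connectivity measure and a two-sided 0.05 test. The documents give no r, so I use 0.2 to 0.4. Per-arm power by Fisher z is p ≈ Φ(arctanh(r)·√(n−3) − 1.96), the opposite tail being negligible. The arms are independent, so the chance of significance in PD-MI only is p(1−p), and the chance that the arms disagree is 2p(1−p).

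Example, r = 0.3 and n = 51: arctanh(0.3) = 0.3095; 0.3095 × √48 = 2.144; p = 0.573; p(1−p) = 0.245.

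| n per arm | r | power per arm | PD-MI only | arms disagree |
|---|---|---|---|---|
| 51 | 0.2 | 0.29 | 0.21 | 0.41 |
| 51 | 0.3 | 0.57 | 0.24 | 0.49 |
| 51 | 0.4 | 0.84 | 0.14 | 0.28 |
| 43 | 0.2 | 0.25 | 0.19 | 0.37 |
| 43 | 0.3 | 0.50 | 0.25 | 0.50 |
| 43 | 0.4 | 0.76 | 0.18 | 0.36 |

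Simulating the Pearson test (40,000 replicates) agrees to about one percentage point; its lowest PD-MI-only figure is 0.13 (n = 51, r = 0.4). The range is therefore 13-25%.

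**Power of the comparison that would answer the question.** I approximate the group-by-connectivity-change interaction by a Fisher z test of r in PD-MI against 0 in PD-Con: z = arctanh(r) / √(2/(n−3)).

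- n = 43, r = 0.3: 0.3095/0.2236 = 1.384, power 28%.
- n = 51, r = 0.3: 0.3095/0.2041 = 1.516, power 33%.
- r = 0.4: power 47% (n = 43) and 55% (n = 51).
- 80% power needs r = tanh(2.80 × 0.2236) = 0.56 at n = 43, and tanh(2.80 × 0.2041) = 0.52 at n = 51.

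**Would a lagged model adjusted for 6-week cognition do better?** Assume that gains are fully maintained, that connectivity change correlates 0.3 with cognition at both 6 and 12 weeks, and that the two cognition scores correlate 0.8 to 0.9. The partial correlation is (0.3 − 0.3·c) / √((1 − 0.09)(1 − c²)):

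- c = 0.8: 0.06/0.572 = 0.105.
- c = 0.9: 0.03/0.416 = 0.072.

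Power with all 86 completers is about 16% and 10%. For comparison, a same-visit correlation of 0.3 has about 80% power at n = 86.

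**The case against.** **It is exploratory.** This is so throughout, and section 3.3 speaks only of a potential link. No success rule or phase 2 decision is tied to Aim 4, and the training effects themselves are compared between arms by group-by-time interaction in Aims 1 to 3. This limits the severity; it does not turn two separate tests into a comparison.

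**The plan does not say that the link is absent in the control arm.** A reader might infer that it does. In section 3.1 the contrast with PD-Con belongs to the sentence on sustained training effects; the link hypothesis is stated for PD-MI alone, and a within-PD-MI test matches it literally. The sentence in section 2.2 on predicting response is about the whole approach, not Aim 4. The plan therefore does not commit to an imagery-specific claim, although the aim's title and the precedent in section 1.2 invite one.

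**Same-day confounding.** A reader might infer that fatigue, mood or medication state on the day would produce the link. The documents do not support so strong a statement. Section 2.3.1 has medicated subjects tested and scanned early in the day on their regular regimen, and section 4.3.2 requires an expected stable regimen. Baseline cognition and baseline fMRI fall on different visits, up to two weeks apart. Neuro-QoL asks about everyday functioning, not performance that day. Some shared influence remains possible: the mood, fatigue and sleep surveys are scheduled once, after screening, and are not repeated at Visit 3. No size can be put on it.

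**The error rates are stylised.** They are for one measure at 0.05. The atlas has 268 nodes, hence 268 × 267/2 = 35,778 pairs, and Aim 4 has no multiplicity rule. At a per-pair threshold of 0.001 and r = 0.3, significance in PD-MI only falls to 8-11% per pair. The overall effect of testing many connections depends on a correction that the plan does not state.

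**Conclusion.** The point holds as a low-cost improvement to an exploratory aim. As written, Aim 4 can support a statement of association within an arm. It cannot support a statement that the association is specific to imagery training, and its same-timepoint pairing does not justify the word prediction.

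The size is a 13-25% chance of significance in PD-MI only when the arms are identical. It rests on an assumed common correlation of 0.2 to 0.4, one pre-chosen measure, an unadjusted 0.05 test, and 43 to 51 completers per arm at the plan's own dropout rates.

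Two stronger readings should be set aside. The primary conclusions are not affected, because they do not depend on Aim 4. Nor does the schedule supply a ready prediction test in the form of 12-week cognition regressed on connectivity change to 6 weeks with adjustment for 6-week cognition. That model addresses only change after training ends, whereas section 3.1 expects gains to be sustained. It would probably be null if gains were simply maintained, and the null could be misread as absence of a mechanism.

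**What to change.** In section 5.4.1, Aim 4:

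1. At each timepoint, fit both arms in one model: cognitive change on group, connectivity change, and their interaction.
2. Report the interaction estimate with its confidence interval. Rest any imagery-specific statement on it, not on one arm being significant and the other not. Per-arm slopes may still be shown.
3. Describe the same-visit results as associations, here and in the matching wording of the Synopsis and sections 3.1, 3.3 and 4.2.2.
4. Name the few connectivity summaries to be used and the multiplicity rule; the power figures above hold only for a single pre-chosen measure.
5. Optionally, add a lagged look (baseline-to-6-week connectivity change against 12-week cognition) as supplementary and exploratory. The version adjusted for 6-week cognition should not serve as the prediction test.

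The cost is analysis-plan wording; every measure is already scheduled at all three timepoints. The real downside is power: 28-33% for 0.3 against 0, with a PD-MI correlation of about 0.52-0.56 needed for 80%. A specific link will be claimed less often, and the plan should say so in advance.
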